6.6.6.2 Columbia–Suicide Severity Rating Scale

The C-SSRS is a clinician-rated instrument that reports the severity of both suicidal ideation and behavior. Suicidal ideation is classified on a 5-item scale: 1 (wish to be dead), 2 (nonspecific active suicidal thoughts), 3 (active suicidal ideation with any methods [not plan] without intent to act), 4 (active suicidal ideation with some intent to act, without specific

plan), and 5 (active suicidal ideation with specific plan and intent). The C-SSRS also captures information about the intensity of ideation, specifically the frequency, duration, controllability, deterrents, and reasons for the most severe types of ideation. Suicidal behavior is classified on a 5-item scale: 0 (no suicidal behavior), 1 (preparatory acts or behavior), 2 (aborted attempt), 3 (interrupted attempt), and 4 (actual attempt). More than 1 classification can be selected provided they represent separate episodes. For actual attempts only, the actual or potential lethality is classified for the initial, most lethal, and most recent attempts. The C-SSRS will be completed at all study visits. At Visit 1 (Screening), the C-SSRS will be completed for the patient's lifetime history of suicidal ideation and behavior, including a 12-month lookback. At all other visits the C-SSRS will be completed for ideation and behavior since the previous visit.

The C-SSRS must be completed by an investigator, subinvestigator or trained rater, all of whom must have extensive professional training.

6.6.6.3 Young Mania Rating Scale

The YMRS ([Young et al, 1978](#)) is an 11-item scale that assesses manic symptoms based on the patient's perception of his or her condition over the previous 48 hours, as well as the physician's clinical observations during the interview. The 11 items are elevated mood, increased motor activity-energy, sexual interest, sleep, irritability, rate and amount of speech, language-thought disorder, content, disruptive-aggressive behavior, appearance, and insight. The severity of the abnormality is rated on a 5-point (0 to 4) or 9-point (0 to 8) scale. Possible scores range from 0 to 60.

This scale will be administered by a trained rater with expertise in evaluating manic patients.

6.7 Summary of Methods of Data Collection

An IWRS will be used to screen patients, dispense IP, randomize patients, and manage IP inventory. All other data for this study will be collected using eCRFs via an electronic data capture system, except for ECG and laboratory data.

A qualified central ECG and central laboratory vendor will be used for the analysis of all ECGs and blood and urine samples. ECG and laboratory data will be transferred to Allergan or its designee on a periodic basis throughout the study.

7 Statistical Procedures

7.1 Analysis Populations

7.1.1 Patient Populations

Four populations will be considered in the statistical analysis of the study.

7.1.1.1 Screened Population

The screened population will consist of all screened patients who sign informed consent.

7.1.1.2 Randomized Population

The randomized population will consist of all patients in the screened population who were randomized to a treatment group.

7.1.1.3 Safety Population

The safety population will consist of all patients in the randomized population who took at least 1 dose of DB IP.

7.1.1.4 Modified Intent-to-Treat Population

The modified intent-to-treat (mITT) population will consist of all randomized patients with ≥ 1 postbaseline assessment of the MADRS total score.

7.2 Collection and Derivation of Primary and Secondary Efficacy Assessments

7.2.1 Primary Efficacy Variable

The primary efficacy parameter is the change from baseline to Week 6 in the MADRS total score.

7.2.2 Additional Efficacy Variables

Additional efficacy parameters will include the following at postbaseline visits described in [Table 1](#):

- Change from baseline in the CGI-S score
- CGI-I score
- CGI-I response (CGI-I score ≤ 2)
- MADRS response ($\geq 50\%$ reduction from baseline in MADRS total score)
- MADRS remission (MADRS total score ≤ 10)
- Change from baseline in the HAMD-17 total score
- Change from baseline in the HAM-A total score

7.3 Hypothesis and Methods of Analysis

All efficacy analyses will be based on the mITT population. Baseline for efficacy is defined as the last nonmissing efficacy assessment before the date of the first dose of DB IP. All statistical hypothesis tests will be 2-sided 5%-level of significance tests for main effects. All confidence intervals (CIs) will be 2-sided 95% CIs, unless stated otherwise.

To compare with historic studies, some analyses based on the imputed data using the last-observation-carried-forward (LOCF) approach, will be presented for all efficacy parameters. Only the postbaseline total score of a parameter will be imputed; individual item scores will not be carried forward. The baseline value will be carried forward only for the intermittent missing values immediately after baseline. If all the postbaseline values are missing, the baseline value will not be carried forward.

7.3.1 Primary Efficacy Analyses

The primary estimand is provided below through specification of the population, the variable, the handling of intercurrent events, and the population-level summary.

Population

The target population are patients with MDD who have had an inadequate response to antidepressant therapy in the current episode and who satisfy the inclusion and exclusion criteria as specified in the protocol.

The analysis population is defined to be the mITT population consisting of all randomized patients with ≥ 1 postbaseline assessment of the MADRS total score as specified in protocol Section 7.1.1.4.

Variable

The variable is the same as the primary efficacy endpoint, which is the change from baseline to Week 6 in the MADRS total score.

Accounting of Intercurrent Events

Intercurrent events and their handling rules are described as follows:

- Regardless of whether allowed rescue medications are taken or not, data are included in the analysis. Patients are still taking assigned drugs as specified in the protocol while taking allowed rescue medications. The clinical objective is to assess the efficacy of the treatment regardless of allowed rescue medication use.
- To evaluate the efficacy at Week 6 in the mITT population, patients are assumed to adhere to the assigned treatment for the duration of the study. As a result, data after the discontinuation from the study treatment due to all reasons will not be included in the primary analysis and they will be assumed as missing at random.

Population-level Summary

The population-level summary for the primary endpoint is the difference in primary variable means between each cariprazine group and placebo.

To address the primary hypotheses that each dose of cariprazine is superior to placebo in the reduction of MADRS total score after 6 weeks of treatment, the change from baseline in MADRS total score will be analyzed using a mixed-effects model for repeated measures (MMRM) with treatment group, country, ADT failure category, visit, and treatment group-by-visit interaction as fixed effects, and the baseline value and baseline-by-visit interaction as the covariates. An unstructured covariance matrix will be used to model the covariance of within-patient scores. The Kenward-Roger approximation ([Kenward and Roger, 1997](#)) will be used to estimate denominator degrees of freedom. In the event of non-convergence of the model using unstructured covariance matrix, a structured covariance matrix will be used in combination with empirical variance estimate (ie, sandwich estimator) to address the potential mis-specified situation. The following sequence of alternative covariance structures (First-order antedependence [ANTE (1)], Toeplitz [TOEP], First-order autoregressive [AR(1)] and compound symmetry[CS]) will be considered in the MMRM until convergence.

The analysis will be performed based on all postbaseline scores using only the observed cases without imputation of missing values. The treatment difference in the primary endpoint

at Week 6 for each active treatment group versus placebo in the mITT population will be estimated and reported along with the corresponding 95% CI and the p-value.

The Hochberg procedure ([Hochberg 1988](#)) will be used to control the overall type I error rate at a 0.05 level (2-sided) for multiple comparisons of 2 active doses with placebo for the primary endpoint. Statistical significance will be determined by comparing the adjusted p-values to $\alpha = 0.050$.

The study will be considered positive if at least 1 dose arm of cariprazine is statistically superior to placebo for change from baseline in MADRS total score at Week 6 after multiplicity adjustment.

A sensitivity analysis using a pattern-mixture model based on non-future-dependent missing value restrictions ([Kenward et al, 2003](#)) will be performed to assess the robustness of the primary MMRM results to the possible violation of the missing-at-random assumption. The details of this sensitivity analyses are as follows:

The pattern for the pattern-mixture model will be defined by the patient's last visit with an observed value. The observed MADRS total score at a visit is assumed to have a linear relationship with the patient's prior measurements. The missing values will be imputed under the assumption that the distribution of a missing observation differs from the observed only by a shift parameter value Δ . The dataset with missing values imputed will be analyzed using an analysis-of-covariance (ANCOVA) model with treatment group, country, and ADT failure category, as factors and baseline MADRS total score as a covariate for between-treatment-group comparison at Week 6. The imputation of missing values and the analysis will be performed multiple times, and the inference of this sensitivity analysis will be based on the combined estimates using the standard multiple imputation technique. The values for Δ will be selected as 0 to 6, inclusively. This range is selected because the mean reduction of MADRS score from baseline within a treatment group at Week 6 is likely to be within 15 points ([Bauer et al, 2009](#); [El-Khalili et al, 2010](#)), and a Δ value of 6 accounts for 40% of treatment efficacy.

The second sensitivity analysis will consider dropout reasons while imputing missing values after the discontinuation. Patients who discontinued due to lack of efficacy in the cariprazine arms are assumed to have no treatment effect after the discontinuation. These patients are assumed to copy the profile of placebo arm and missing values are imputed based on the distribution estimated from the placebo group under the MAR using copy-reference approach ([Carpenter et al, 2013](#)). The rest of missing values in the placebo arm and cariprazine arms

will be imputed using the observed data in their respective group under the MAR assumption.

Mean treatment difference (raw mean difference \pm standard error) in change in primary endpoint between each cariprazine dose and placebo with missing values imputed using the LOCF approach will be plotted against country. In addition, summary statistics will be provided by center to examine the consistency of treatment effect across the study centers.

The impact of dropouts on the efficacy outcomes will be explored graphically by plotting the time courses of mean changes by dropout reason.

Results of analyses from MMRM and from ANCOVA models will also be reported for each visit between baseline and Week 6.

To compare with historic studies, the LOCF approach will be used with an ANCOVA model that has treatment group, country and ADT failure category as factors and the baseline value as the covariate.

7.3.2 Other Efficacy Analyses

Additional quantitative efficacy parameters will be analyzed in the following way:

Analysis of CGI-I score, change from baseline in HAMD-17 total score, change from baseline in HAM-A total score, and change from baseline in CGI-S will be performed using a similar MMRM to that used for the primary analysis. Baseline CGI-S score will be used as a covariate for the analysis of change in CGI-I score. In addition, these parameters will be analyzed using ANCOVA (with LOCF imputation) as used for the analysis of primary efficacy parameters.

Additional categorical efficacy parameters will be analyzed in the following way:

Rates for categorical parameters (response and remission) will be reported by treatment group and by visit; a logistic regression model (with LOCF imputation) will be used to model the probability of a response or the probability of a remission as a function of a treatment group and the corresponding baseline score (CGI-S for the analysis of the CGI-I response) as explanatory variables.

7.3.3 Safety Analyses

The safety analysis will be performed using the safety population. The safety parameters will include AEs, clinical laboratory parameters, vital signs, ECG parameters, EPS scales, the C-SSRS and the YMRS. For each safety parameter, the last assessment made before the first dose of DB IP will be used as the baseline for all analyses of that safety parameter. The summarization will be by treatment group for both double-blind and safety follow-up periods.

7.3.3.1 Adverse Events

An AE will be considered a treatment-emergent adverse event (TEAE) if the AE began or worsened (increased in severity or became serious) on or after the first dose of DB IP.

For the DB treatment, the number and percentage of patients reporting TEAEs in each treatment group will be tabulated by system organ class and preferred term; by system organ class, preferred term, and severity; and by system organ class, preferred term, and relationship to the IP. If more than 1 AE is coded to the same preferred term for the same patient, the patient will be counted only once for that preferred term using the most severe and most related occurrence for the summarization by severity and by relationship to the IP.

The distribution of TEAEs by severity and relationship to the IP will be summarized by treatment group.

The TEAEs during the safety follow-up period will be summarized by body system, preferred term, and treatment group for the safety population.

An AE that occurs more than 30 days after the date of the last dose of DB IP will not be summarized.

The number and percentage of patients with common ($\geq 2\%$ of patients in any treatment group) TEAEs, on-therapy SAEs, and AEs leading to premature discontinuation of IP will be summarized by preferred term and treatment group and sorted by decreasing frequency for the test treatment. An SAE will be defined as an on-therapy SAE if it occurred on or after the date of the first dose of DB IP and within 30 days of the date of the last dose of DB IP.

Listings will be presented for patients with SAEs, patients with AEs leading to discontinuation, and patients who die (if any). All patients with SAEs, including SAEs reported during the screening period and the safety follow-up period, and patients

discontinuing because of AEs occurring before the start of DB IP will be included in these listings.

The number and percentage of patients reporting TEAEs of ocular events of special interest will be summarized. A listing of all reported ocular events of special interest will be provided.

7.3.3.2 Clinical Laboratory Parameters

Descriptive statistics for clinical laboratory values (in SI units) and changes from the baseline values at each assessment time point will be presented by treatment group for each clinical laboratory parameter. In addition, descriptive statistics for values and changes from the baseline values in conventional units at each assessment time point will be presented for selected clinical laboratory parameters; these will be detailed in the statistical analysis plan (SAP).

The number and percentage of patients with potentially clinically significant (PCS) postbaseline clinical laboratory values will be tabulated by treatment group. The criteria for PCS laboratory values will be detailed in the SAP. The percentages will be calculated relative to the number of patients with available non-PCS baseline values and at least 1 postbaseline assessment. The numerator will be the total number of patients with available non-PCS baseline values and at least 1 PCS postbaseline value. A supportive listing of patients with PCS postbaseline values will be provided, including the patient identification number, study center number, and baseline and postbaseline values. A listing of all AEs occurring in patients who have PCS laboratory values will also be provided.

The number and percentage of patients with treatment-emergent significant changes in lipid parameters (total cholesterol, low-density lipoprotein cholesterol, high-density lipoprotein cholesterol, and triglycerides) and glucose will be tabulated by treatment group for the DB treatment period. The criteria for treatment-emergent significant changes in lipids and glucose will be detailed in the SAP. Percentages will be calculated relative to the number of patients with baseline values meeting the specified baseline criteria and with at least 1 postbaseline assessment. The change in lipids and glucose from baseline to the highest (lowest for high-density lipoprotein cholesterol) postbaseline measurement will be summarized. Supportive listings of patients with treatment-emergent changes in lipids and glucose values will be provided.

The number and percentage of patients meeting potential Hy's Law criteria will be tabulated by DB treatment group starting from the first dose of DB IP to within 30 days after the last dose of DB IP for the safety population. A supportive listing will be provided.

7.3.3.3 Vital Signs

Descriptive statistics for vital signs and changes from baseline values at each visit and at the end of the DB treatment period will be presented by treatment group.

Vital sign values will be PCS if they meet both the observed-value criteria and the change from baseline value criteria. The criteria for PCS vital sign values will be detailed in the SAP. The percentages will be calculated relative to the number of patients with baseline values and at least 1 postbaseline assessment. The numerator will be the total number of patients with available baseline values and at least 1 PCS postbaseline value. A supportive listing of patients with postbaseline PCS values will be provided, including the patient identification number, study center number, and baseline and postbaseline values. A listing of all AEs occurring in patients who have PCS vital sign values will also be provided.

The number and percentage of patients with orthostatic hypotension will be provided by treatment group. Orthostatic hypotension is defined as a reduction of ≥ 20 mm Hg in systolic BP or a reduction of ≥ 10 mm Hg in diastolic BP measured after the patient stands up after resting in the supine position. Standing measurements should be taken after a sufficient amount of time has passed to allow the BP to equilibrate in the standing state. A supportive listing will be provided including the patient identification number, study center number, and baseline and postbaseline systolic and diastolic BP values (supine and standing).

The definition of different hypertension status will be detailed in the SAP.

Tabulations showing the number and percentage of patients with hypertension status changes from baseline will be provided for:

- Shift of hypertension status from baseline to end of the DB treatment period
- Shift of hypertension status from baseline to highest category during the DB treatment period

Supportive listings of patients who have a shift in hypertension status from normotensive/prehypertension at Baseline to stage I/stage II hypertension will be provided.

7.3.3.4 Electrocardiogram

Descriptive statistics for ECG parameters (ie, heart rate, PR interval, QRS interval, RR interval, QT interval, QTcB, and QTcF) and changes from baseline values at each assessment timepoint will be presented by treatment group.

The number and percentage of patients with PCS postbaseline ECG values will be tabulated by treatment group. The criteria for PCS ECG values will be detailed in the SAP. The percentages will be calculated relative to the number of patients with available non-PCS baseline values and at least 1 postbaseline assessment. The numerator will be the total number of patients with available non-PCS baseline values and at least 1 PCS postbaseline value. A supportive listing of patients with PCS postbaseline values will be provided, including the patient identification number, study center number, and baseline and postbaseline values.

In addition, a listing of all AEs occurring in patients who have PCS ECG values and a listing of patients with clinically significant postbaseline ECG abnormalities, as reported by the Investigator and/or the central ECG laboratory, will also be provided.

The number and percentage of patients with a change from baseline QTc > 30 msec but not exceeding 60 msec, and of patients with an increase > 60 msec will be tabulated by treatment group. A supportive listing that includes the patient identification number, study center number, all QTc values (including change from baseline values), and all AEs will be provided for all patients who have postbaseline QTc changes > 30 msec.

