10.4 ELECTROCARDIOGRAM

Descriptive statistics for ECG parameters (heart rate, RR interval, PR interval, QRS interval, QT interval, QTcB interval, and QTcF interval) and changes from baseline values at each assessment time point to the end of the DB treatment period will be presented by treatment group. The QTc will be calculated using both the Bazett and Fridericia corrections (if the vendor does not provide).

Electrocardiographic parameter values are considered PCS if they meet or exceed the higher-limit PCS criteria listed in Table 10-4. The number and percentage of participants with PCS postbaseline ECG values will be tabulated by treatment group for the double-blind treatment period. The percentages will be calculated relative to the number of participants with available non-PCS baseline values and at least 1 postbaseline assessment for the double-blind treatment period. The numerator is the total number of participants with available non-PCS baseline values and at least 1 PCS postbaseline value for the double-blind treatment period. A supportive tabular display of participants with PCS postbaseline values will be provided, including the participant identification (PID) number, baseline, all postbaseline (including non-PCS) values, and change from baseline.

In addition, a tabular display showing all AEs that occurred in participants who had postbaseline PCS ECG values will be provided.

A shift table from baseline to the end of study in the Investigator's overall interpretation of the ECG will be presented by treatment group for the following categories: normal; abnormal, not clinically significant; abnormal, clinically significant. A tabular display showing participants with postbaseline clinically significant ECG abnormalities according to the Investigator's overall interpretation will be provided.

Table 10-4 Criteria for Potentially Clinically Significant Electrocardiograms

Parameter	Unit	Higher Limit
QRS interval	msec	≥ 150
PR interval	msec	≥ 250
QTc (QTcB or QTcF) interval	msec	>500
QTc (QTcB or QTcF) interval	msec	Increase of > 60

QTc = QT interval corrected for heart rate.

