16.2 SAFETY AND OTHER EVALUATIONS

This section specifies analyses related to COVID-19 pandemic from the following aspects:

- COVID-19 Status
- Disposition
- Demographics and Other Baseline Characteristics
- Study visit (missing entire visit due to COVID-19 or missing assessments due to COVID-19)
- Protocol deviation
- Study drug interruption(s) due to COVID-19
- TEAEs related to COVID-19 infection

Safety Population will be used for the planned analyses in this section described above, unless stated otherwise.

The number of participants impacted by COVID-19 during the study and COVID-19 status will be summarized by treatment group. In addition, the number of participants impacted by COVID-19 and their corresponding disposition status in the double-blind treatment period and the follow-up period will be summarized respectively.

Baseline characteristics (including demographic, baseline disease characteristics, and relevant medical history) will be summarized relative to the onset of pandemic (date of randomization \leq Mar 11, 2020 vs. date of randomization $>$ Mar 11, 2020).

The number of participants who missed at least one entire visit due to COVID-19 will be summarized by treatment group. Furthermore, the number of participants who missed at least one assessment due to COVID-19 will be summarized by assessment category (laboratory, vital signs, ECG, C-SSRS, YMRS, EPS scales) and by visit.

The number of participants with significant protocol deviation due to COVID-19 will be provided. The number of participants with any COVID-19 related treatment interruption(s) will be provided as well.

The number of participants with TEAEs related to COVID-19 infection will be provided.

Supporting listings for the above described analyses will be provided. Furthermore, a listing of TEAEs leading to study discontinuation related to COVID-19 will be provided.

17.0 **CHANGES TO ANALYSES SPECIFIED IN PROTOCOL**

In Section 11.0 (Health Outcome Analyses), the term “Study center” in the ANCOVA model for analyzing PCS-12 and MCS-12 will be replaced with terms country and ADT failure category to align with the analyses for other efficacy endpoints.

In Section 10.1 (Adverse Events), AE summary timeframe was modified to align with AE reporting period specified in the protocol amendment 1. The new time frame is defined below:

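### SAP 10.4 omits the protocol's by-arm count of QTc increases above 30 and up to 60 msec and its listing of changes above 30 msec, and no section of the SAP declares the omission

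*Protocol*

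**What the plan says.** **Protocol 7.3.3.4.** Two QTc outputs are fixed in the protocol itself. The first counts, arm by arm, those showing a "change from baseline QTc > 30 msec but not exceeding 60 msec" and, separately, those who rise by more than 60 msec. The second is a supportive listing in which all QTc values and "all AEs will be provided for all patients who have postbaseline QTc changes > 30 msec". Only the PCS thresholds are left to the later document: "The criteria for PCS ECG values will be detailed in the SAP".

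**SAP 10.4 and Table 10-4.** The rule is "Electrocardiographic parameter values are considered PCS if they meet or exceed the higher-limit PCS criteria listed in Table 10-4". For QTc, that table has two rows: a value above 500 msec, and "Increase of > 60". Patient-level output follows the same definition: "A supportive tabular display of participants with PCS postbaseline values will be provided", and the accompanying AE display covers the same PCS participants. The section also keeps by-arm descriptive statistics for QTcB and QTcF with changes from baseline, and a shift table of the Investigator's ECG interpretation.

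**SAP 17.0 (Changes to Analyses Specified in Protocol).** Three changes are declared: the SF-12 model terms, the AE time frame ("AE summary timeframe was modified to align with AE reporting period specified in the protocol amendment 1"), and the replacement of the on-therapy SAE definition. No ECG item appears. Appendix III, which summarises the major changes in SAP Amendments 1 and 2, has none either.

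**The concern.** The protocol sets the 30 and 60 msec cut points outside the PCS framework, so the SAP's authority to define PCS criteria does not extend to removing them. A programmer working from SAP 10.4 as written would produce neither the intermediate category nor the listing triggered at 30 msec. A reader of SAP 17.0 would not learn that a protocol output had gone, although that section records a change as small as a model term for the SF-12.

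At stake is one descriptive cardiac-safety output. A patient whose QTc rises by 30 to 60 msec without passing 500 msec would be counted in no QTc category, and would reach the linked AE display only by qualifying on some other ECG parameter. No hypothesis test and no efficacy result depends on it.

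**Working it through.** **Step 1. Set the two sections side by side.**

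| Output | Protocol 7.3.3.4 | SAP 10.4 |
|---|---|---|
| Mean QTcB/QTcF change by arm | yes | yes |
| Increase above 30 and up to 60 msec, count by arm | yes | absent |
| Increase above 60 msec, count by arm | yes | yes, as a PCS criterion |
| QTc above 500 msec | left to the SAP as a PCS criterion | yes |
| Listing with QTc values and AEs, change above 30 msec | yes | absent; displays cover PCS participants only |

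Two protocol outputs have no counterpart, and neither absence is declared in SAP 17.0 or Appendix III.

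**Step 2. Does the 500 msec row cover the gap?** Exclusion criterion 19 removes men with a screening QTcF of 450 msec or more and women with 470 msec or more. Scheduled ECGs are at Visit 1 and Visit 6/ET only (Protocol 6.6.5), so the screening ECG is normally the baseline.

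- A man enters at 449 msec or less. A rise of 31 to 50 msec takes him to at most 449 + 50 = 499 msec. He is not above 500, and his increase is not above 60.
- A woman with a baseline of 440 msec or less and a rise of 31 to 60 msec reaches at most 440 + 60 = 500 msec. She is also not above 500, and her increase is not above 60.

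Both meet neither retained QTcF criterion, so the 500 msec row does not stand in for the missing band. This check is for QTcF only, because the exclusion limit is stated for QTcF and a QTcB value could still qualify.

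**Step 3. How many patients might be involved?** The documents state no expected count, event rate or SD for QTc change, so there is no plan figure to reproduce. The following is illustrative. Assume a normal change with mean m and SD s, one post-baseline ECG per patient, and n = 250 per arm (SAP 13.0).

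- Expected in band = n × [Φ((60 − m)/s) − Φ((30 − m)/s)]
- Expected above 60 = n × [1 − Φ((60 − m)/s)]

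Worked case, m = 0 and s = 20: Φ(3) − Φ(1.5) = 0.99865 − 0.93319 = 0.0655, and 250 × 0.0655 = 16.4. Above 60: 1 − Φ(3) = 0.00135, and 250 × 0.00135 = 0.34.

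| Assumed SD (msec) | 30–60, m = 0 | > 60, m = 0 | 30–60, m = +5 | > 60, m = +5 |
|---|---|---|---|---|
| 12 | 1.6 | 0.00 | 4.7 | 0.00 |
| 15 | 5.7 | 0.01 | 11.9 | 0.03 |
| 20 | 16.4 | 0.34 | 25.7 | 0.74 |
| 25 | 26.7 | 2.05 | 36.2 | 3.48 |
| 30 | 34.0 | 5.69 | 42.2 | 8.34 |

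The band holds between 42.2/(42.2 + 8.34) = 0.835 and nearly all of the patients above 30 msec. With the planned 15% dropout and no ECG from those patients (250 × 0.85, about 212 per arm), the ranges become 1.3 to 35.8 in the band and 0 to 7.1 above 60.

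**The case against.** The case for leaving the SAP alone has real content.

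- **A mean shift remains visible.** SAP 10.4 keeps mean QTcB and QTcF change by arm. A reader might infer that the SAP has removed the only output able to show a dose-related QTc shift. The documents do not support that: comparing mean changes across arms does so without any category.
- **The data are not lost.** SAP 15.3 says that all assessments will appear in the data listings. What is missing is the by-arm tabulation and the listing filtered at 30 msec with AEs attached.
- **The > 60 msec category need not be empty.** A reader might also infer that what remains would hold almost no patients. That is true only under an assumption: fewer than 1 patient per arm at an SD of 20 msec or less, but about 2 to 3.5 at 25 msec and 5.7 to 8.3 at 30 msec. Nothing in the documents says which applies. The denominator is also uncertain: early-termination ECGs are planned, remote COVID-19 visits may omit the ECG, and unscheduled ECGs may occur.
- **It may not be a decision.** SAP 3.0 presents the SAP as an elaboration of the protocol and puts table and listing specifications in a separate document that is not available here. The outputs may be specified there, so deliberate deletion cannot be inferred.

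These points limit the consequence. They do not remove the mismatch: the SAP text does not carry two outputs that the protocol promised, and the section meant to declare departures is silent. A separate output specification would not supply that declaration.

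**Conclusion.** The point holds as a minor reconciliation between protocol and SAP. The omission of the 30 to 60 msec tabulation and of the listing above 30 msec, and the lack of any declaration, follow from the text alone and need no assumption. The conclusion that the 500 msec row does not fill the gap rests on the stated exclusion limits and on the screening ECG serving as baseline.

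The size is illustrative: about 2 to 42 of 250 patients per arm in the omitted band against 0 to 8 above 60 msec, over an assumed SD of 12 to 30 msec and a mean shift of 0 to +5 msec. Across that range, the band contains roughly 84% or more of all patients above 30 msec. The counts do not show that either category would, or would not, detect a drug effect.

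**What to change.** In the text of SAP 10.4, separately from the PCS criteria, add the by-arm number and percentage of participants with a QTcB or QTcF increase above 30 and up to 60 msec and above 60 msec. Add also the listing of all QTc values and AEs for every participant with a change above 30 msec.

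The new category should not be placed in Table 10-4. That table defines PCS values, so a row there would turn every increase above 30 msec into a PCS event and enlarge the PCS counts and displays, which the protocol does not ask for.

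If the sponsor means to drop these outputs, SAP 17.0 should say so and give the reason. If the separate output specification already contains them, SAP 10.4 should be brought into line with it.

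The cost is one small table and one listing from data already collected.
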